(defined as whatever communication system the child uses) will avoid having to ask the child if he/she is physically able to sign his/her name. Verbal assent will be documented on the assent form.

Many participants 18 to <21 years of age who are their own guardians may have the motor ability to sign their own names. Therefore, if a participant is 18 to <21 years of age and his/her own guardian and is unable to physically sign his/her name, the researchers request an alteration of consent and would like to request that verbal consent be obtained rather than signed consent. Verbal consent will be documented on the consent form.

Additional Criteria: Additional Information to Participants

Whenever appropriate, the participants will be provided with additional pertinent information after participation. Explain how this will be accomplished or why this cannot be done.

All information related to the study will be provided to all participants prior to the onset of any data gathering activities.

Additional Criteria: Identifiable Private Information/Biospecimens Does this research involve identifiable private information or identifiable biospecimens?

No

- 8. Research Procedures and Methods
- 8. Research Procedures and Methods
- 8a. Frequency and Time Involvement

Describe the frequency and length of time subjects will be involved in the study.

The focused physical therapy examination will take 90-120 minutes. Each training session will take approximately 60 minutes. An additional 30-45 minutes will be added to the final training session. The single follow-up session will take 45-60 minutes. The total time involved in the study is between 8 hours, 45 minutes and 12 hours, 45 minutes.

8b. Description of Intervention/Data Collection

Describe step-by-step what will occur during your project, including any intervention(s). Include a description of the data you are collecting (i.e., the specific variables, the specific tests/surveys, data collection instruments, etc.), how it will be collected, and how it will be analyzed.

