Research Design: The research design to be employed in the proposed is a single-arm, open label study without a control group involving the following components: (a) Baseline examination and baseline/pre-intervention testing (T0); (b) A three-week intervention period consisting of two, 60-minute PWC skills training sessions per week; (c) Post-intervention testing completed immediately after the completion of the intervention period (T1); and (d) A single session retention trial held 4 weeks after the completion of the intervention period (T2).

Prior to the onset of any data collection activities, [name] will obtain ethically valid consent, permission, and assent as appropriate using the procedures previously outlined in this document.

Prior to the onset of data collection, [name] as a licensed physical therapist will perform a focused physical therapy examination to determine whether the participant would best be able to drive using a joystick or switch(es) as well as how and where the joystick or switch(es) should be placed to best accommodate each participant's needs. Per the standards of the physical therapy profession, this examination will include obtaining a complete medical history via parental interview (this interview will not be recorded) and a systems review (including a screen of cardiopulmonary, integumentary, musculoskeletal, and neurological systems). Obtaining a complete medical history and completing the review of systems for each potential participant

will allow [name] to determine if it is safe for each potential participant to partake in power mobility training. The switches or joystick used will be placed on each participant's manual wheelchair only when he or she is driving and will not result in any permanent changes to the participant's manual wheelchair.

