TO data collection activities will also take place during this focused physical therapy evaluation. A demographic form will be completed. The primary outcome measure will be the Assessment of Learning Powered mobility use (ALP), a process-based assessment instrument reflecting the process of understanding how to use a PWC. Secondary outcome measures pertaining to PWC skill execution included the Wheelchair Skills Checklist (WSC) and the Canadian Occupational Performance Measure (COPM). A focused, two question parent/caregiver interview will be conducted and digitally recorded. The interview questions will be: 1) Can you describe (your child's name) for me?; and 2) How do you think your child will respond to power mobility training? Follow-up prompts to these two main questions will include the parent's perceived benefits and challenges of power mobility training for his/her child. Once parent-report data collection activities are completed, participant's power mobility skills will be assessed by [name], a licensed physical therapist. The child will use the IndieTrainer during administration of the ALP and the WSC.

Participants will then partake in 2 training sessions per week over a 3-week period. NOTE: Should training sessions be cancelled due to child illness or inclement weather, missed training sessions will be rescheduled during the 3-week period. If this cannot be accomplished, the 3-week time period will be extended for up to 7 days. This 7-day extension would only be used when necessary to ensure the child's health, well-being, and safety.

A parent or guardian must accompany the child participant to each training session. Participants will be video-taped and photographed while using the IndieTrainer. These photographs and videos will allow the licensed physical therapist researcher ([name]) to determine how each participant is responding to the IndieTrainer program and will help he licensed physical therapist researcher ([name]) to determine when to progress a participant to the next stage of IndieTrainer program. As noted in the consent/permission form, the GVSU research team may ask permission to use photographs or videos in professional presentations or publications. In such instances, permission (and assent if applicable) would be obtained via a separate Video and Photography Release Authorization Form.

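### Does the stated maximum participation time of 12 h 45 min put the amount of training in doubt?

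*Combined protocol and SAP*

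**What the plan says.** Section 8a lists four timed components. For baseline, "The focused physical therapy examination will take 90-120 minutes". For training, "Each training session will take approximately 60 minutes". A further 30 to 45 minutes is added to the last training session, and one follow-up visit takes 45 to 60 minutes. The section then gives the total: "The total time involved in the study is between 8 hours, 45 minutes and 12 hours, 45 minutes".

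Section 8a does not give the number of sessions. Section 8b does so twice. The research design paragraph has "A three-week intervention period consisting of two, 60-minute PWC skills training sessions per week", and the procedures that follow have "Participants will then partake in 2 training sessions per week over a 3-week period". Section 8b also says that T0 "data collection activities will also take place during this focused physical therapy evaluation", so baseline testing is not a separate visit. If sessions are cancelled, "missed training sessions will be rescheduled during the 3-week period"; failing that, "the 3-week time period will be extended for up to 7 days". Neither provision adds a session.

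**The concern.** The upper limit of the total cannot be reached from the components listed beside it. The gap is a round 3 hours, and 12 h 45 min is exactly what six 90-minute sessions or nine 60-minute sessions would give at the upper limits of the other components. A reader could therefore suspect that the figure preserves a different training schedule, with up to half as much training again as the design describes.

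If so, the matter would go beyond addition. Training is the exposure whose effect the T0 to T1 change is meant to show, and doubt about its amount would make the result harder to interpret and to repeat. If instead the total is simply wrong, the review board has been given an overstated time burden, in a study where a parent or guardian must attend every training session.

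**Working it through.** **Inputs** (minutes)

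- Baseline examination, including T0 testing: 90 to 120 (8a; 8b for the inclusion of T0)
- Training: 2 sessions per week × 3 weeks × 60 = 360 (8b; session length also in 8a)
- Addition to the final session: 30 to 45 (8a)
- Follow-up: 45 to 60 (8a)

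**The plan's own figures**

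- Minimum: 90 + 360 + 30 + 45 = 525 = 8 h 45 min. The stated minimum is reproduced.
- Maximum: 120 + 360 + 45 + 60 = 585 = 9 h 45 min. The stated maximum is 12 h 45 min = 765, so it is not reproduced.
- Excess: 765 − 585 = 180 minutes; 180 / 585 = 31%.
- Width of the range: the components can differ by only 30 + 15 + 15 = 60 minutes between their limits, whereas the stated limits differ by 765 − 525 = 240.

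**Can another training schedule explain the total?**

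With the other components at their upper limits (120 + 45 + 60 = 225), the stated maximum leaves 765 − 225 = 540 minutes, and 540 / 360 = 1.5. This is the source of the apparent 50% extra training. It requires the whole excess to be training time, which the document nowhere says.

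- Six sessions of 90 minutes, or nine of 60: the maximum is 225 + 540 = 765, which fits. The minimum is 90 + 540 + 30 + 45 = 705 = 11 h 45 min, which contradicts the stated 8 h 45 min.
- The end-of-training addition applied to every session: 120 + 6 × (60 + 45) + 60 = 810 = 13 h 30 min, or with 30 minutes, 120 + 6 × 90 + 60 = 720 = 12 h 00 min. Neither fits.
- Six sessions of 60 to 90 minutes, or six to nine sessions of 60 minutes: 525 to 765. Both limits fit, but neither range appears in the document.

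No fixed alternative of this kind reproduces both limits. Only a range does, and the text states none.

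**Does anything use the total?**

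The justification for 25 dyads in section 6a(iii) uses an effect size of 1.48, alpha of 0.05, 90% probability and 10% attrition. The Data Analysis part of 8b uses scores at T0, T1 and T2, with its thresholds set on ALP phase and COPM points. Neither refers to total participation time.

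**The case for a change.** The strongest case for acting is that the contradiction is certain, sits in the account of time given to the review board, and costs one line to repair. Because a range of 60 to 90 minutes per session would reproduce both limits, the total may have been carried over from another session length. The document alone cannot exclude that, and its authors could fairly be asked. All of this stands.

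The step from there to doubt about the training exposure does not stand. The schedule is stated consistently wherever it is described, and the lower limit of the total was evidently built from it. Someone repeating the study would follow the design paragraph in 8b, not work back from a total in 8a. A plain slip in the upper limit explains the discrepancy at least as well as an unstated schedule. If the components are as intended, the error overstates the burden, so families would give less time than stated; that is still inaccurate, but it is the less harmful direction.

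Recording delivered training minutes for each child may be useful in its own right, but an addition error is no reason to require it. The consent form was not available, so whether it repeats the figure is unknown.

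**Conclusion.** The arithmetic criticism is correct: the stated maximum is 180 minutes (31%) above the sum of its components, and the minimum is exact. The wider criticism fails. The 50% increase in training is a conditional reading that the text does not make, and the fixed schedules offered for it contradict the stated minimum.

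This is a clerical inconsistency in a derived administrative figure. The total in 8a has to be reconciled with the session number and length in 8a and 8b, as ordinary editing; the document does not show how the discrepancy arose. Sample size, power, error rate, endpoints and analysis would all be the same afterwards, so no change to the plan is called for.

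This rests on two assumptions: that 8a and 8b together list every timed activity, and that rescheduled sessions replace missed ones and are not extra.

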 What type of review do you believe your project falls under?
 Expedited
 6. Subject Population
 6a. Subject Population Description
 6a(i). Number of Subjects

6a(ii). Subject Population Characteristics

Briefly describe the subject population characteristics (i.e., age ranges, and where appropriate, gender, ethnic background, and health status).

Participants will be children (defined as 3 to <21 years of age) with cerebral palsy or other similar conditions who have mobility limitations (e.g., function at Gross Motor Function Classification System Level IV or V), are unable to functionally self-propel a manual wheelchair, and who do not have an individually prescribed powered wheelchair. Other inclusion criteria include: parent report that the child has beginning cause and effect skills (e.g. the child responds to games such as peek-a-boo or activates toys through motor activities such as pressing, hitting, batting, or squeezing), age =5 years and <21 years old, child currently uses a manual wheelchair or adaptive stroller that can be safely used with the IndieTrainer system (i.e. functioning wheel brakes to remain locked onto platform, etc.), and the ability to attend to visual stimuli as assessed by [name] (to ensure that the child was able to attend to the videogame activities) as assessed by [name]. Exclusion criteria include any condition or issue that would prevent a child from safely using the IndieTrainer system as determined by [name]. The child and his/her wheelchair combined must also weigh <300 pounds to safely use the IndieTrainer.

6a(iii). Number of Subjects Justification

Provide a justification for why the number of subjects to be recruited is appropriate.

A sample size of 25 child-parent dyads was determined using an estimated effect size (Cohen's d) of 1.48 for T0 to T1 changes in the primary outcome measure, a significant within group difference at alpha = 0.05 with a 90% probability, and a 10% dropout/attrition rate, as based on our previous work.

6b. Vulnerable Populations

Will any vulnerable populations be recruited for this study? These include, but are not limited to, children under the age of 18, prisoners, mentally disabled persons, economically disadvantaged, or pregnant persons.

Yes

6b(i). Vulnerable Population Justification

Indicate the vulnerable population(s) to be recruited.

Children under the age of 18

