After completion of the final session, T1 testing will occur and will include re-administration of the ALP, the WSC, and the COPM. A focused, two question parent/caregiver interview will be conducted and digitally recorded. The interview questions will be: 1) Can you describe (your child's name) for me? How do you think your child responded to power mobility training? Follow-up prompts to these two main questions will include the parent's perceived benefits and challenges of power mobility training for his/her child. In addition, parents' impressions of the IndieTrainer system will be gathered using the Client Satisfaction Questionnaire (CSQ-8).

T2 testing will involve administration of the ALP and the WSC.

Data Analysis:

Frequency counts will be used to report categorical demographic variables. We will use SAS Studio 5.1 (SAS Institute Inc., Cary, NC, USA) to calculate descriptive statistics for continuous demographic variables and CSQ-8 total scores and to perform all statistical analyses. If appropriate, we will use parametric tests in our analyses. We will use a one-way repeated measures ANOVA to assess differences in ALP and WSC scores at T0, T1, and T2 at 0.05 α level. Post-hoc paired samples two-tailed t-test with a Bonferroni correction will be used as appropriate to assess mean differences between T0 and T1, T0 and T2, and T1-T2. Mean COPM Performance and Satisfaction scores will be assessed via a paired samples two-tailed t-test at 0.05 α level. Frequency counts for total CSQ-8 scores will be reported. The clinical significance of changes between T0 and T1 will be assessed using the following guidelines: an improvement of at least one ALP phase and an increase of ≥2 points in COPM performance. Cohen's d effect sizes will be interpreted as small = 0.20 to 0.49; moderate = 0.50 to 0.79; and large ≥0.80.

Data from the parent/guardian interviews will be transcribed verbatim by the researchers. Qualitative data will be analyzed using the Linguistic Inquiry and Word Count program (LIWC 2015), a text analysis program. LIWC 2015 examines each word in a transcript against an internal dictionary of 6,000+ words to place each word into appropriate linguistic and psychological categories and can objectively evaluate a transcript based on 4 summary language

variables: Analytical Thinking, Clout, Authenticity, and Emotional Tone.

8c. Compensation

Will subjects be compensated for their participation in the study?
No

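### Cheap improvement: the trial is sized on the ALP T0-T1 change at alpha 0.05 but tests it only as one of three Bonferroni-corrected post-hoc contrasts, which is valid but needlessly strict

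*Combined protocol and SAP*

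**What the plan says.** - **Primary outcome** (section 8b, T0 data collection): "The primary outcome measure will be the Assessment of Learning Powered mobility use (ALP").
- **Sizing** (section 6a(iii)): "A sample size of 25 child-parent dyads was determined using an estimated effect size (Cohen's d) of 1.48". The target is "T0 to T1 changes in the primary outcome measure, a significant within group difference at alpha = 0.05 with a 90% probability", with 10% attrition allowed for.
- **Main test** (section 8b, Data Analysis): "We will use a one-way repeated measures ANOVA to assess differences in ALP and WSC scores at T0, T1, and T2", at 0.05.
- **Test of the sized contrast** (same paragraph): "Post-hoc paired samples two-tailed t-test with a Bonferroni correction will be used as appropriate to assess mean differences between T0 and T1". T0-T2 and T1-T2 complete the list. No contrast is singled out as primary. The divisor is not given, nor is it said whether F must be significant first.
- **Other mention of T0-T1**: "The clinical significance of changes between T0 and T1 will be assessed using the following guidelines: an improvement of at least one ALP phase". This is a descriptive guideline and sets no test level.
- **Role of T2** (section 8b, Research Design): "A single session retention trial held 4 weeks after the completion of the intervention period (T2").

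The only paired t-test planned at an unadjusted 0.05 is for COPM, a secondary outcome.

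**The concern.** The sample size section has one contrast and one alpha in mind. The analysis section gives that contrast no special standing and, on the natural reading, tests it at a third of that alpha. The contrast and level used for sizing are therefore not those of any planned ALP test.

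Two things are at stake. If the true T0-T1 effect is smaller than planned, the correction costs power on the main question. And plain Bonferroni holds T0-T2 and T1-T2 at 0.05/3 even when T0-T1 is overwhelmingly significant, which costs power on the retention question at the sponsor's own planning effect.

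**Working it through.** **Inputs.** From section 6a(iii): d = 1.48, alpha 0.05, power 90%, 25 dyads, 10% attrition. Completers: 25 × 0.9 = 22.5, taken as 22. From section 8b: two-tailed paired t-tests on three contrasts. Assumed: divisor 3, and d standardised by the SD of the paired differences.

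**1. The plan's own figure.** A paired two-sided t-test at d = 1.48 and alpha 0.05 reaches 90% power with 7 completers; 7/0.9 = 7.8, so 8 enrolled. At 0.05/3 it needs 10; 10/0.9 = 11.1, so 12 enrolled. Neither gives 25. Of the variants tried at alpha 0.05, only a two-independent-group calculation does (11 per group, 22 in total, 22/0.9 = 24.4, so 25), and that is not the design described. This is a separate matter.

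**2. T0-T1 power, 22 completers.** The noncentrality is d√n, with 21 degrees of freedom. The critical t is 2.080 at 0.05 and 2.601 at 0.05/3. For d = 1.48, d√n = 1.48 × 4.690 = 6.94, far beyond both.

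| d | at 0.05 | at 0.05/3 |
|---|---|---|
| 1.48 (plan) | >0.9999 | >0.9999 |
| 0.8 (assumed) | 0.95 | 0.86 |
| 0.6 (assumed) | 0.77 | 0.59 |
| 0.5 (assumed) | 0.61 | 0.42 |

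The effect detectable with 90% power is 0.73 at 0.05 and 0.84 at 0.05/3. If ALP and WSC contrasts were pooled (divisor 6), power at d = 0.8 would be 0.79.

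**3. Is a less strict rule valid?** Rule A tests T0-T1 at 0.05 and, only if it is significant, T0-T2 and T1-T2 each at 0.05.
- If T0 = T1, no rejection of any kind can occur unless T0-T1 is falsely rejected, so family-wise error is at most 5%.
- If T0 ≠ T1, then T0 = T2 and T1 = T2 cannot both hold. At most one true null is left, tested at 5%.

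Family-wise error is therefore controlled without a further correction. Simulation gave 4.7-5.2% under the global null and every partial null (22 completers, 40,000 runs per scenario). Four covariances were assumed: compound symmetry 0.6; autoregressive 0.7; T1-T2 correlation 0.9 with 0.3 elsewhere; and SDs 1, 1.5, 1.5 with correlation 0.6.

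**4. T2 contrasts at d = 1.48, half the gain retained (assumed).**

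| Contrast, covariance | Bonferroni | Rule A |
|---|---|---|
| T0-T2, compound symmetry | 0.80 | 0.91 |
| T0-T2, autoregressive | 0.53 | 0.72 |
| T1-T2, compound symmetry | 0.80 | 0.91 |
| T1-T2, unequal variances | 0.69 | 0.84 |

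Holm over all three contrasts, with no gate, comes within 0.01 of Rule A in these cases.

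**5. What the gate can cost.** At d = 1.48, nothing. At an assumed d = 0.5 with T2 at twice the T1 gain (compound symmetry), T0-T2 power falls from 0.98 to 0.61. With no T1 effect and a T2 shift of d = 1.0, it falls from 98% to 5%.

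**The case against.** The strongest reply is that nothing fails at the trial's own inputs. Bonferroni over three contrasts is valid and stricter than the sizing alpha, and T0-T1 power at d = 1.48 is about 1.00 either way. All of this stands. A reader might infer that the correction leaves the trial short of its 90% power, or that N should rise; the documents' own effect size rules out both. The T0-T1 gains depend on smaller effects, and the T2 gains on retention and covariances, that the documents do not give.

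It is also true that the T2 gain at d = 1.48 comes from dropping plain Bonferroni, not from naming a primary contrast, since Holm alone delivers it. What naming T0-T1 adds is power for that contrast at smaller effects: at d = 0.5 with the gain fully retained (compound symmetry), 0.61 against 0.45 under Holm.

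The gate is a real cost. It makes the retention question depend on T1. The plan gives little reason to expect benefit only at T2, because training ends before T1 and T2 is described as a retention trial, but the choice should be deliberate. In a single-arm, open-label study, raising the T0-T1 false-positive rate from about 1.7% (0.05/3) to the nominal 5% also deserves a conscious decision.

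A reader might further take the ANOVA to be a compulsory gate. The text does not say so.

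**Conclusion.** The point holds as a low-cost improvement, optional to recommended; it is not an error in the plan. The contrast and alpha used for sizing are not carried into the analysis, and the Bonferroni rule gives up power that can be recovered with family-wise error still at 5%. At the planning effect the gain is confined to the T2 contrasts: 0.80 to 0.91 under compound symmetry with half the gain retained. For T0-T1 the gain is insurance against a smaller effect: 0.86 to 0.95 at d = 0.8, and 0.42 to 0.61 at d = 0.5.

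These figures rest on 22 completers, a divisor of 3, no F gate and the assumed covariances. Two neighbouring issues add no weight. The plan says "If appropriate, we will use parametric tests in our analyses" and names no fallback for the primary contrast, which is a separate missing detail. And aligning contrast and alpha does not explain N = 25, which the stated paired inputs do not reproduce.

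**What to change.** Amend the Data Analysis part of section 8b before outcome data are analysed:

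1. Name ALP T0-T1 as the single primary comparison: a paired two-sided t-test at 0.05, not conditional on the omnibus F.
2. If it is significant, test ALP T0-T2 and T1-T2 each at 0.05 with no further correction.
3. Keep the repeated measures ANOVA as supportive.
4. Report all three differences with 95% confidence intervals whatever the test results.

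If the sponsor does not want the T2 contrasts to depend on T0-T1, replace Bonferroni with Holm over all three contrasts. Holm controls the same family-wise error, never rejects less than Bonferroni, and gives the same T2 gains at d = 1.48 to within 0.01.

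The cost is wording only: no change to N, visits or data. The gated rule's price is the higher T0-T1 false-positive rate and the loss of formal T2 tests when T0-T1 fails; the estimates and intervals would still be reported.
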